4.7 Safety Analyses

The safety and tolerability will be summarized by descriptive statistics for the SAF population.

4.7.1 Adverse Events

AEs will be coded using MedDRA and graded using the National Cancer Institute-Common Terminology Criteria for Adverse Events (NCI-CTCAE version 5.0).

A TEAE is defined as an AE observed after administration of the IP and up to the follow-up period. An IP-related TEAE is defined as any TEAE with a causal relationship assessed as "yes" by the investigator.

The number and percentage of participants with TEAEs, IP-related TEAEs, serious TEAEs and IP-related serious TEAEs will be summarized by system organ class, preferred term and dose level. The worst grade will be summarized if the same AE is recorded more than once for a participant.

AE data will be listed.

An overview table will include the following by tumor type and dose level:

- TEAEs
- Drug related TEAEs
- Serious TEAEs

- Drug related serious TEAEs
- TEAEs leading to death
- TEAEs of Interest: Hypersensitivity SMQ by NCI-CTC Grade
- Drug-related TEAEs leading to death
- Deaths
- Drug-related Grade 3 or higher TEAE
- Drug-related Grade 3 or higher: Local Site Reaction
- Drug-related Grade 3 or higher: Infusion Related Reactions
- Drug-related Grade 3 or higher: Hypersensitivity SMQ

4.7.2 Clinical Laboratory Evaluation

For quantitative clinical laboratory measurements, descriptive statistics will be used to summarize results and change from baseline by dose level and time point.

Shifts from baseline to the post baseline worst grade based on NCI-CTCAE until the follow up period in clinical laboratory tests will be tabulated. Quantitative laboratory test results by NCI-CTCAE Grade (version 5.0) will be summarized with frequencies and percentages by dose level and time point.

Laboratory data will be listed.

4.7.3 Liver Safety Assessment

The liver safety assessments will be summarized by the categories below based on the measurements from Alkaline Phosphatase (ALP), Alanine Transaminase (ALT), Total Bilirubin, Aspartate Transaminase (AST) and their combination. These parameters will be based on measurements from a local laboratory.

The participant's highest value during the course of the study will be used; upper limit of normal (ULN).

- ALT: > 3xULN, > 5xULN, > 10xULN, > 20xULN
- AST: > 3xULN, > 5xULN, > 10xULN, > 20xULN
- ALT or AST: > 3xULN, > 5xULN, > 10xULN, > 20xULN
- ALP: > 1.5xULN
- Total Bilirubin: > 2xULN
- (ALT or AST > 3xULN) and Total Bilirubin > 2xULN
- (ALT or AST > 3xULN) and Total Bilirubin > 2xULN and ALP < 2xULN

The last 2 criteria where 2 or more parameters are evaluated will use the measurements on the same day or up to 1 day apart. The number and percentage of subjects meeting the criteria post-baseline will be summarized.

Information on alcohol, other substance use will be listed by dose level and tumor type.

ISN/Protocol 5354-CL-1201

4.7.4 Vital Signs

Descriptive statistics will be used to summarize vital sign results and changes from baseline by dose level and time point. Vital signs data will be listed.

A table for potentially clinically significant vital signs (blood pressure >150/90 mmHg or <70/60 mmHg; pulse > 100 per min or <60 per min; respiratory rate <12 and >16) will be generated by tumor type and dose level.

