5.2 Exclusion Criteria

Participant will be excluded from participation in the study if any of the following apply:

1. Participant has had prior LN surgery in the area where LN detection is needed.
2. Participant has had prior LN radiation in the area where LN detection is needed.
3. Participant has had prior neo-adjuvant chemotherapy.
4. Participant has definitive LN metastases.
5. Participant has metastatic cancer.
6. Participant has received any investigational therapy within 28 days or 5 half-lives, whichever is longer, prior to screening.

7. Participant has any condition, which, in the investigator's opinion, makes the participant unsuitable for study participation.
8. Participant has a known or suspected hypersensitivity to ASP5354, ICG or any components of the formulation used.
9. Participant has had previous exposure to ASP5354.
10. Participant has moderate to severe cardiac disease that limits daily functioning (New York Heart Association Class III-IV) or other medical conditions that the investigator feels would impact safety or study compliance.
11. Participant has a resting heart rate ≤ 45 bpm or ≥ 115 bpm, systolic blood pressure ≥ 160 mmHg or diastolic blood pressure ≥ 100 mmHg within 1 week prior to IP administration. If the blood pressure exceeds the limits above, repeat readings can be taken. Participant who has adequately controlled blood pressure is eligible.
12. Participant has any of the following screening laboratory values:
 - Hemoglobin ≤ 9 g/dL
 - Absolute neutrophil count $\leq 1500/\mu\text{L}$
 - Platelet count $\leq 100000/\mu\text{L}$
 - Estimated glomerular filtration rate $< 60 \text{ mL/min}/1.73 \text{ m}^2$ based on the Chronic Kidney Disease Epidemiology Collaboration equation*
 - Serum bilirubin $\geq 1.5 \times$ upper limit of normal (ULN)
 - Aspartate aminotransferase (AST) $\geq 2.5 \times$ ULN
 - Alanine aminotransferase (ALT) $\geq 2.5 \times$ ULN

*eGFR = $141 \times \min(\text{Scr}/\kappa, 1)^\alpha \times \max(\text{Scr}/\kappa, 1) - 1.209 \times 0.993 \text{Age} \times 1.018$ [if female] $\times 1.159$ [if African American]

where:

Scr is serum creatinine in mg/dL,

κ is 0.7 for females and 0.9 for males,

α is -0.329 for females and -0.411 for males,

min indicates the minimum of Scr/ κ or 1, and

max indicates the maximum of Scr/ κ or 1

13. Participant has received ICG, other NIR-F imaging agents, Blue dye (e.g., methylene blue or isosulfan blue) or Magtrace within 2 weeks prior to IP administration.

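### SAP 4.7.4: the respiratory-rate flag cannot be met as written, and the vital-sign table does not say that only post-dose values count

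*SAP*

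**What the plan says.** SAP 4.7.4 defines three criteria in one sentence:

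- "blood pressure >150/90 mmHg or <70/60 mmHg"
- "pulse > 100 per min or <60 per min"
- "respiratory rate <12 and >16"

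The first two join a high and a low limit with *or*; the third uses *and*, and gives no unit. On layout, the SAP says only that the table "will be generated by tumor type and dose level". It does not mention visits, baseline or post-dose values.

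The same section has two other outputs. Descriptive statistics will "summarize vital sign results and changes from baseline by dose level and time point", and "Vital signs data will be listed".

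The section just before it, SAP 4.7.3 on liver safety, does state its period: "The number and percentage of subjects meeting the criteria post-baseline will be summarized".

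Protocol 5.2, exclusion criterion 11, sets the entry limits: "Participant has a resting heart rate ≤ 45 bpm or ≥ 115 bpm", or systolic pressure of 160 mmHg or more, or diastolic pressure of 100 mmHg or more, within a week before dosing. It sets no limit on respiratory rate and no lower limit on blood pressure.

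**The concern.** A table of this kind exists to count individuals whose values cross a limit, which means and standard deviations can mask. Respiratory rate is a named part of the secondary safety endpoint (Protocol Table 3). If its criterion is programmed literally, its row shows zero whatever the data. If the programmer interprets it, the result depends on a choice that the SAP does not record.

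The missing time points raise a second question. Vital signs are taken before and after dosing, and the entry criteria are wider than the table's limits. A count by dose level could then mix values that predate the drug with values that followed it. Dose levels hold 3 to 12 participants, so a few such cases can change the picture between doses.

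**Working it through.** The plan states no figure on this point, so there is none to reproduce. The check applies the written rules to whole-number values.

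**1. Respiratory rule (SAP 4.7.4).** A flagged value x must satisfy x < 12 and x > 16. That set is empty. The possible readings differ:

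| Reading | What is flagged |
|---|---|
| Literal, per measurement | nothing |
| Two limits in a list (*or*) | 11 or lower, 17 or higher |
| Across visits within a participant | one visit at 11 or lower and another at 17 or higher |

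**2. Time points (Protocol Table 1).** Vital signs are scheduled at screening, preoperatively, postoperatively and on day 10: two before dosing and two after. If screening is done on day 1, there is one before dosing. SAP 4.7.4 does not say which of these enter the table.

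**3. Overlap of entry limits and table limits.**

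- Pulse: criterion 11 admits 46 to 114, which is 114 − 46 + 1 = 69 whole-number values. The table flags 46–59 (14 values) and 101–114 (14 values), so 28 of 69. This counts values, not participants.
- Systolic: admitted below 160 and flagged above 150, so 151–159 overlap.
- Diastolic: admitted below 100 and flagged above 90, so 91–99 overlap.
- The blood-pressure rule does not say whether one or both components must exceed the limit. A reading of 155/80 is flagged if either suffices and not flagged if both are needed. A reading of 155/95 is flagged on both readings.
- Respiratory rate has no entry limit, so any rate outside 12–16 may be present before dosing.

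**4. Weight of one participant.** One participant with a steady pulse of 55 adds 1/3 = 33% at a dose level of 3 and 1/12 = 8% at a dose level of 12, with no change after dosing.

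**5. Why changing one word is not enough.** This illustration uses assumed figures that are not in the documents: respiratory rate normal with mean μ of 14 to 18 and SD σ of 2 to 3 breaths/min, independent visits and no drug effect. With *or*, the chance that one value is flagged is

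p = Φ((11.5 − μ)/σ) + 1 − Φ((16.5 − μ)/σ),

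and the chance of at least one flag in k visits is 1 − (1 − p)^k.

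| μ, σ | p | Any of 4 visits | Any of 2 post-dose visits |
|---|---|---|---|
| 14, 2 | 0.211 | 0.613 | 0.378 |
| 16, 3 | 0.501 | 0.938 | 0.751 |
| 18, 2 | 0.774 | 0.997 | 0.949 |

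Over the six combinations of μ (14, 16, 18) and σ (2, 3), p runs from 21% to 77%, any of four visits from 61% to 99.7%, and either of two post-dose visits from 38% to 95%. The across-visit reading of *and* would flag 0.2% to 32%. Correlation between a participant's visits would lower the any-visit figures. Under these assumptions the result depends heavily on both the reading and the visits counted, and background flags remain common even after dosing. That is why baseline status should be shown.

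**The case against.** The strongest reply is that this is a one-word slip that any programmer would read as a list of two limits. The table formats sit in separate specifications (SAP 4.1) that are not available here. That is fair. An empty row follows from the literal rule; it is not a prediction of what will be produced. It remains true that the SAP does not state the intended reading.

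A reader might infer that respiratory abnormalities would be hidden. The documents do not support this. SAP 4.7.4 lists all vital-sign data and summarizes results and changes by time point, and Protocol 10.3.1.1 makes clinically significant vital-sign abnormalities reportable as adverse events. Nor does the flaw disable monitoring for hypersensitivity. SAP 4.7.1 has dedicated hypersensitivity outputs, and Protocol Table 1 calls for histamine and tryptase sampling after a reaction. No intraoperative vital signs are scheduled, so even a corrected table would be a weak detector of an acute reaction.

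A reader might also infer that participants who are normal at entry are wrongly counted. They are not: someone within limits at entry and flagged later is a genuine new finding. The difficulty lies with those already outside a limit.

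The entry ranges are not exactly the baseline ranges. Criterion 11 allows repeat blood-pressure readings and admits controlled blood pressure, and baseline is the last value before dosing (SAP 4.2). The overlap therefore shows what is possible, not how often it occurs.

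Finally, restricting the table to participants within limits at baseline would lose those who start slightly outside and worsen, such as a pulse of 102 before dosing and 150 after. That objection stands, and the fix respects it.

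**Conclusion.** Wrong as written, with small impact. The respiratory criterion cannot be met by any single measurement, and the *or* used for the other two signs marks it as a drafting error. The table also leaves its time points open, so pulse or blood-pressure values beyond the limits before dosing can be counted as if they were findings. For blood pressure, this partly depends on the unstated one-or-both rule.

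The first conclusion is a matter of logic and needs no assumption beyond the literal, per-measurement reading. The second rests on the SAP's silence about visits and on criterion 11; how many participants it touches cannot be known from the documents.

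Only this descriptive table is affected. No hypothesis is tested, and the optimal-dose assessments listed in SAP 4.3.1 do not include it. Protocol 4.1 lets the review committee consider safety data, but neither document says that this table is supplied to it.

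**What to change.** In SAP 4.7.4:

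1. Change *and* to *or* in the respiratory-rate criterion, giving <12 or >16, and add the unit.
2. State that the table counts post-dose values only.
3. Show baseline status beside the post-dose count, for example as a baseline-by-post-dose shift layout, keeping participants who were already outside a limit at baseline.
4. State whether one or both blood-pressure components must cross the limit.

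The limits themselves are for the sponsor to confirm. The cost is one word, a few sentences in the SAP and minor programming. No new data are needed, because baseline is already defined in SAP 4.2 and the visits are already scheduled.

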4.7.5 Electrocardiograms

The routine 12-lead ECG results and intraoperative ECG monitoring will be summarized by dose level and time point.

12-lead ECG and intraoperative ECG data and interpretations will be listed.

4.7.6 COVID-19 Impact Assessment

Assessments affected by the COVID-19 pandemic will be listed for visit-based assessments and for non-visit-based assessments.

For visit-based assessments affected by COVID-19, the listing shows if an assessment was not performed due to COVID-19, if it was out of window, if the assessment was performed at an alternative location or if it was a virtual assessment. Other information and comments reported on assessments affected by COVID-19 are also included.

For non-visit-based assessments affected by COVID-19, subjects who experience any of the following items: COVID-19 adverse event, hospitalization due to COVID-19, or COVID-19 death, will be flagged in a listing.

Any events like adverse events, hospitalization, or death, which are related to COVID-19, will be flagged in the corresponding listing.

4.8 Analysis of PK

PK analysis will be conducted on the PKAS.

4.8.1 Estimation of PK parameters

The plasma PK parameter calculation will be performed using noncompartmental method in Phoenix® (Certara St. Louise, MO, USA, version 6.3 or higher) software. For AUC determination, linear up and log down analysis will be used.

4.8.2 Plasma Concentration and PK parameters

Plasma concentrations and PK parameters of ASP5354 will be summarized by tumor type and dose level and, where appropriate, by nominal time points and days using descriptive statistics, including n, mean, SD, coefficient of variation (CV), geometric mean, geometric CV, median, minimum and maximum. For the pharmacokinetic parameters t_{max} only n, median, minimum and maximum will be calculated. For induction phase nominal days for Ctrough concentration based on start of ASP5354 administration will be used.

ISN/Protocol 5354-CL-1201

4.8.3 Analysis of Pharmacokinetics

A listing and summary statistics of the individual plasma concentrations of ASP5354 and sampling times by treatment and assessment time interval will be prepared.

4.9 Interim Analysis

VRC review will be held after the initial 3 participants in 0.2 mg in each tumor type have data for review. Three participants each will then be enrolled in the 2 additional dose levels in each tumor type. The determination of dose(s) to stop, continue or define as optimal dose will start when 3 participants assigned to each dose level have their data for visualization reviewed by the VRC. This process will continue for every additional 3 participants assigned to each dose level until reaching the maximum of 12 participants. A new dose level might be added.

4.10 Sample Size Determination

The sample size is not based on statistical power calculation. The sample size is expected to provide adequate information to determine the optimal dose ASP5354 for LN visualization in breast cancer and melanoma. Approximately up to 12 participants will be assigned to each 3 dose levels of ASP5354 in each tumor type, and then an estimated total of up to 36 participants will be required in each tumor type. In case some dose levels are stopped based on VRC, additional dose levels might be added.

4.11 Additional Conventions

4.11.1 Missing Data

As a general principle, no imputation of missing data will be done. Exceptions are the start and stop dates of AEs and concomitant medications if they are missing

In case of missing or partial start and stop dates for concomitant medications, the following rules will be used:

If the start date is missing or partial:

- if the month is missing, use January
- if the day is missing, use the first day of the month under consideration
- if the year is missing, use year of the informed consent date
- if the entire date is missing, use informed consent date

If the stop date is missing or partial:

- if the month is missing, use December
- if the day is missing, use the last day of the month under consideration
- if the year or the entire date is missing, set the stop date to December 31st, 2099

If the imputed start date is after the stop date, then the imputed start date will be 1 day prior to the stop date.

For AEs, a missing or incomplete onset date will be imputed according to the following conventions.

ISN/Protocol 5354-CL-1201

If only the year is known for the AE onset date, the imputed onset date will be the latest of the following non-missing dates:

- Date of first dose of study drug
- January 1 of the year of AE onset date

If only the month and year is known for the onset date, set the surrogate onset date to the first day of that month and then apply the following rules.

- If the month and year of the onset date is prior to the month and year of the first dose of study drug, then the surrogate onset date will be the imputed onset date.
- If the month and year of the onset date is on or after the month and year of the first dose of study drug, then the imputed onset date will be the latest of the following non-missing dates:
 - Date of first dose of study drug
 - Surrogate onset date

If the imputed onset date is after the adverse event end date, the imputed onset date will be the same as the adverse event end date.

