1 PROTOCOL SUMMARY

1.1 Synopsis

Title of Study:

A Phase 2 Open-label, Dose-finding Study to Determine the Optimal Dose for Lymph Node Visualization using ASP5354 in Participants with Breast Cancer or Melanoma Undergoing Sentinel Lymph Node Biopsy

Planned Study Period:

From approximately 3Q2021 to 1Q2025.

Planned Total Number of Study Sites and Location(s):

Approximately 4 study sites in the US

Study Objectives, Endpoints and Estimands:

Objectives	Endpoints
Primary	
• To determine the optimal dose of locally administered ASP5354 for LN visualization in participants undergoing SLN biopsy• Optimal dose determination by the VRC based on:
○ LN tissue visualized (Yes/No)○ Visualized tissue is lymphatic in origin based on pathologic confirmation○ The Likert Scale determination of the intensity of fluorescence (0 to 3)○ Proportion of identified LN with histopathologic confirmation of LN tissue by ASP5354 compared with SoC treatment with either Tc-99mSC (approved drug) or Lymphoseek® (generic name tilmanocept)
Secondary	
• To evaluate LN visualization of locally administered ASP5354 in participants undergoing SLN biopsy• Proportion of participants with at least 1 LN detected by visualization (Yes/No) with histopathologic confirmation of LN tissue using ASP5354• To compare LN detection for ASP5354 with the technetium-based treatment in breast cancer and melanoma• Proportion of identified LN with histopathologic confirmation of LN tissue by ASP5354 compared with SoC treatment with either Tc-99mSC or Lymphoseek
Table continued on next page	

Objectives	Endpoints
Secondary (continued)	

• To investigate the safety and tolerability of locally administered ASP5354 in participants undergoing SLN biopsy	
• Vital signs (blood pressure, pulse and respiratory rate)• Standard 12-lead ECGs• Clinical laboratory tests (hematology [complete blood count], serum chemistry and urinalysis)• Nature, frequency and severity of TEAEs and SAEs

• To investigate the pharmacokinetics of locally administered ASP5354 in participants undergoing SLN biopsy	
• Plasma concentrations of ASP5354
Exploratory	

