7.3 Adverse Events and Other Safety Aspects

The definitions of an AE, SAE or ADE can be found in [Sections [10.3.1](#) Definition of Adverse Events, [10.3.2](#) Definition of Serious Adverse Events and [10.3.3](#) Adverse Device Effect], respectively.

AEs will be reported by the participant (or, when appropriate, by a caregiver, surrogate, or the participant's legally authorized representative), investigator (surgeon) or anesthesiologist.

The investigator and any qualified designees are responsible for detecting, documenting and recording events that meet the definition of an AE, SAE or ADE and remain responsible for following up AEs that are serious, considered related to the study, or that caused the participant to discontinue the IP and/or study [see Section [10.3](#) Appendix 3 Adverse Events/Adverse Device Effects: Definitions and Procedures for Recording, Evaluating, Follow-up and Reporting].

The method of recording, evaluating, and assessing causality of AE, SAE and ADE and the procedures for completing and transmitting SAE/ADE reports are provided in [Section [10.3](#) Appendix 3 Adverse Events/Adverse Device Effects: Definitions and Procedures for Recording, Evaluating, Follow-up and Reporting].

7.3.1 Time Period and Frequency for Collecting Adverse Event and Serious Adverse Event Information

All SAEs will be collected from the signing of the ICF until the follow-up visit at the time points specified in the Schedule of Assessments [[Table 1](#)] and reported on the eCRF.

All AEs will be collected from the signing of the ICF until the follow-up visit at the time points specified in the Schedule of Assessments [[Table 1](#)] and reported on the eCRF.

If the NCI CTCAE grade of an SAE/AE changes, the event should be relisted on the eCRF with the new NCI CTCAE grade and new onset date.

If the NCI CTCAE grade decreases, the SAE/AE should be relisted on the eCRF with the new NCI CTCAE grade and new onset date. The exception is ongoing pre-dose events that continue post-dose and improve post-dose. Such events should not be re-listed.

If the NCI CTCAE grade of an SAE reduces, the details of the AE should be provided on the SAE worksheet for the medical assessor to be able to assess the course of the event.

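### The year-only rule for adverse event onset moves an event from a year before dosing to the dosing date, unless its recorded end date is before dosing

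*SAP*

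**What the plan says.** SAP 4.11.1 gives two rules for incomplete adverse event onset dates, followed by a cap.

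- **Year only.** "If only the year is known for the AE onset date, the imputed onset date will be the latest of the following non-missing dates". The two candidates are "Date of first dose of study drug" and "January 1 of the year of AE onset date". There is no condition on whether the known year comes before the dosing year.
- **Month and year.** The onset is provisionally set to the first of the known month. The rule then branches: "If the month and year of the onset date is prior to the month and year of the first dose of study drug", that provisional date is kept. Otherwise the later of first dose and the provisional date is used.
- **Cap.** "If the imputed onset date is after the adverse event end date", the onset is reset to the end date.

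SAP 4.7.1 defines treatment emergence: "A TEAE is defined as an AE observed after administration of the IP and up to the follow-up period". Protocol 7.3.1 starts collection before dosing: "All AEs will be collected from the signing of the ICF until the follow-up visit". The schedule of assessments (Protocol 1.3, Table 1) places screening on Days -28 to -1, and a note to the table also allows it on Day 1.

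**The concern.** Imputing to first dose is a sensible cautious choice when the known part of a date leaves open whether the event began before or after dosing. When the known year is earlier than the dosing year, nothing is left open: the recorded data already show that the event began before dosing. The year-only rule overrides that information. The month-and-year rule, a few lines later, respects it. The same event can therefore be classified in opposite ways, with the less complete date giving the later onset.

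Such events can occur. Adverse events are recorded from consent, and the planned study period ("From approximately 3Q2021 to 1Q2025") crosses four year-ends. The grade-change instructions in Protocol 7.3.1 also provide for events that are ongoing before dosing and continue after it. At stake is a pre-dose event appearing in the treatment-emergent tables of dose groups that start at 3 participants and reach at most 12 per tumor type (SAP 4.9 and 4.10).

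**Working it through.** The plan states no figure to reproduce here. The check applies the rules literally.

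**Rule in symbols.** Let D be the first dose date and Y the known onset year. The year-only onset is max(D, 1 January Y). If an end date E is recorded and the imputed onset is later than E, the onset becomes E. When Y is before the year of D, 1 January Y is always before D, so the maximum is always D.

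**Example.** D = 10 January 2023, Y = 2022, so max(10 Jan 2023, 1 Jan 2022) = 10 Jan 2023. Applying the cap:

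| Recorded end date | Imputed onset under the SAP | Position relative to dosing |
|---|---|---|
| none | 10 Jan 2023 | dosing date |
| 15 Jan 2023 | 10 Jan 2023 | dosing date |
| 10 Jan 2023 | 10 Jan 2023 | dosing date |
| 4 Jan 2023 | 4 Jan 2023 (cap) | before dosing |
| 28 Dec 2022 | 28 Dec 2022 (cap) | before dosing |

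The same event recorded as December 2022 goes through the month-and-year rule, is imputed to 1 December 2022, and stays before dosing.

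**All dosing dates.** Reading the planned period as 1 July 2021 to 31 March 2025 gives 184 + 365 + 365 + 366 + 90 = 1370 possible dosing dates. With no end date, a prior-year event is moved to the dosing date on all 1370.

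**How often it could arise.** Assume that dosing dates are spread evenly. Screening of up to 28 days can cross a year-end only for dosing on 1 to 28 January. The period contains four Januaries:

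- Upper bound: 4 × 28 = 112 dates, and 112/1370 = 8.2%.
- If consent is also uniform over Days -28 to -1, dosing on day d of January crosses the year-end for 29 − d of the 28 possible consent days. Summed over d = 1 to 28 this is 406, and 4 × 406/(28 × 1370) = 4.2%.

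These are shares of participants whose screening could cross a year-end. They are not rates of the error, which also needs an event starting between consent and 31 December, a year-only onset, and no end date before dosing. The documents give no rate for those.

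**Size of one case.** SAP 4.7.1 counts participants. One extra participant adds 1/12 = 8.3 percentage points in a group of 12 and 1/3 = 33.3 in a group of 3, provided that participant is not already counted in that row.

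**The case against.** The strongest reply is that the section already contains a safeguard and that little is left after it. A reader might infer from the year-only rule alone that every prior-year event becomes treatment-emergent. The cap prevents that: an event with a recorded end date before dosing is put back before dosing, as the last two rows of the table show. This part of the objection stands and limits the point to events that are ongoing, have no end date, or end on or after dosing.

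Three other strong readings also go too far.

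- **That the SAP expressly classes these events as treatment-emergent.** It does not say how an imputed onset on the dosing date, with no clock time, is handled. Counting it as treatment-emergent is the evident purpose of imputing to first dose, but it is an inference.
- **That each case shifts a rate by 8 to 33 points.** It does so only in rows where the participant has no other qualifying event.
- **That dose selection could be affected.** Protocol 4.1 lists safety data among what the Visualization Review Committee considers, but neither document says that the committee works from tables built on imputed onset dates. SAP section 2 plans no hypothesis test.

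It is also fair to say that year-only dates should be uncommon when events are collected prospectively over about 10 days per participant (Protocol 1.1), and that Day 1 screening reduces the reach further. None of this removes the inconsistency: for the remaining events the rule returns a date that the recorded year rules out.

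**Conclusion.** Wrong as written, and minor. For a year-only onset in a year before dosing, the rule always selects the dosing date before the cap is applied. The result stands for any event without a recorded end date before dosing. That such an event is then tabulated as treatment-emergent rests on the evident intent of the rule.

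The reach is small: at most about 8% of dosing dates, or about 4% with uniform consent timing, in both cases assuming evenly spread dosing and before requiring a year-only date. The effect is confined to descriptive safety tables, where the small dose groups make a single misplaced participant visible. This is a correction worth making because it is almost free. It is not a threat to the study's conclusions.

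**What to change.** Give the year-only rule the pre-dose branch that the month-and-year rule already has. If the known onset year is before the year of first dose, impute 1 January of the known year; otherwise use the later of first dose and 1 January of that year. Leave the month-and-year rule and the cap unchanged.

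Using the first day of the known period matches the month-and-year rule. The imputed date may precede consent, but it serves only to place the event before dosing. The branch should not carry a consent-date lower bound. Consent in the new year would move the onset out of the recorded year again, and consent on Day 1 would put it back on the dosing date.

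With the branch added, the example gives 1 January 2022 for every end date in the table, and none of the 1370 dosing dates yields an onset on or after dosing. The cost is one sentence in the SAP and one line of code, with no change to data collection.
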